### 3.2.1 Intention-To-Treat (ITT) Population

The intention-to-treat population (ITT) will consist of all randomized subjects who received at least one dose of study drug, irrespective of the dose actually received. Subjects will be analyzed in the treatment group assigned at randomization. Subjects will be included in a particular analysis, for a particular population, if relevant data is available for analysis (e.g., the primary analysis will require both Baseline and at least one post-Baseline GA measurement, to calculate a change score).

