### 7.2 ANALYSIS OF PRIMARY EFFICACY ENDPOINT

The primary efficacy endpoint is mean rate of change in GA over 12 months measured by fundus autofluorescence (FAF) at three time points: Baseline, Month 6, and Month 12. To eliminate the dependency of GA growth rates on the Baseline lesion size (Feuer et al., 2013), instead of using the observed GA area measurement, the square root of the GA area will be used in the analysis.

For analyses of the primary endpoint, a Mixed-Effects Repeated Measures (MMRM) model will be used to assess the differences between the treatment groups in rate of change of GA area over 12 months. Two separate models will be fitted for comparing Zimura 4 mg vs. Sham control, and Zimura 2 mg vs. Sham control. Both models will be fitted by using restricted maximum likelihood (REML) and include Baseline VA (< 50 letters vs.  $\geq 50$  letters), size of the Baseline GA (< 4 disc area vs.  $\geq$  4 disc area), and pattern of FAF at the junctional zone of GA (none/focal vs. banded/diffuse) as used in the randomization as covariates. For Zimura 2 mg vs. Sham control model, fixed effects will include treatment, visit, part (Part 1 vs. Part 2), the Baseline VA (< 50 letters vs.  $\geq$  50 letters), size of the Baseline GA (< 4 disc area vs.  $\geq$  4 disc area), pattern of FAF at the junction zone of GA (none/focal vs. banded/diffuse), treatment by visit interaction, and the stratification factors by visit interactions. For Zimura 4 mg vs. Sham control model, the same fixed effects will be used excluding part (Part 1 vs. Part 2). An unstructured (co)variance structure will be used to model the within-subject errors. If this analysis fails to converge, alternative structures (e.g., heterogeneous autoregressive or heterogeneous compound symmetry, in this order) will be considered. The Kenward-Roger approximation will be used to estimate denominator degrees of freedom. The test of the mean rate of change over 12 months will be assessed by testing the appropriate contrast of the model parameter estimates.

In addition to the analyses described above, a similar analysis will be conducted using the observed GA area measurement.

The analyses described above will also be repeated in a supportive manner for the PP population.

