### 7.3 ANALYSIS OF SECONDARY EFFICACY ENDPOINTS

Two secondary efficacy endpoints are pre-specified:

- Mean change in best corrected visual acuity (ETDRS letters) from Baseline to Month 12
- Mean change in low luminance best corrected visual acuity (ETDRS letters) from Baseline to Month 12

Secondary efficacy analysis will be conducted for ITT population for these pre-specified secondary endpoints. The analyses described above will also be repeated in a supportive manner for the PP population.

[figure not shown]
Descriptive tables will be provided for secondary endpoints based on the observed data, but due caution will be exercised in interpreting descriptive tables because of the potential impact of missing data. Sensitivity analyses of the secondary endpoints will also be performed (see Section 7.6).

Any hypothesis testing performed as part of analyzing secondary efficacy endpoints will be considered exploratory.

For analyses of the secondary endpoints, a Model for Repeated Measures (MRM) will be used to assess the differences between the treatment groups at month 12 visit. The model will be fitted by using restricted maximum likelihood (REML). The model will include Baseline VA (< 50 letters vs.  $\geq$  50 letters), size of the Baseline GA (< 4 disc area vs.  $\geq$  4 disc area), and pattern of FAF at the junctional zone of GA (none/focal vs. banded/diffuse) as used in the randomization as covariates. Fixed effects will include treatment, visit, part (Part 1 vs. Part 2), the Baseline VA (< 50 letters vs.  $\geq$  50 letters), size of the Baseline GA (< 4 disc area vs.  $\geq$  4 disc area), pattern of FAF at the junction zone of GA (none/focal vs. banded/diffuse), treatment by visit interaction, and the stratification factors by visit interactions for Zimura 2 mg vs. Sham control model. For Zimura 4 mg vs. Sham control model, the same fixed effects will be used excluding part (Part 1 vs. Part 2). An unstructured (co)variance structure will be used to model the within-subject errors. If this analysis fails to converge, alternative structures (e.g., heterogeneous autoregressive or heterogeneous compound symmetry, in this order) will be considered. The Kenward-Roger approximation will be used to estimate denominator degrees of freedom. Significance tests will be based on appropriate treatment contrasts at month 12.

CONFIDENTIAL

7.4	
-	
-	
_	

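### SAP 7.2 and 7.3 name covariance fallbacks without a standard error robust to a wrong structure: this can narrow the Month 12 visual acuity intervals and, on one reading of SAP 7.2, leaves the primary level unassured

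*SAP*

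**What the plan says.** For the primary endpoint, SAP 7.2 specifies a REML repeated-measures model: "An unstructured (co)variance structure will be used to model the within-subject errors". Its fallback is "If this analysis fails to converge, alternative structures (e.g., heterogeneous autoregressive or heterogeneous compound symmetry, in this order) will be considered". Inference is model-based: "The Kenward-Roger approximation will be used to estimate denominator degrees of freedom". The readable text names no empirical (sandwich) standard error.

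SAP 7.2 does not say what the response vector is. It describes GA "measured by fundus autofluorescence (FAF) at three time points: Baseline, Month 6, and Month 12" and states that "the square root of the GA area will be used in the analysis", which could mean three raw values per eye. The contrast is not written out either: "The test of the mean rate of change over 12 months will be assessed by testing the appropriate contrast of the model parameter estimates". SAP 3.2.1, however, says "the primary analysis will require both Baseline and at least one post-Baseline GA measurement, to calculate a change score", which points to two change scores, at Months 6 and 12.

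SAP 7.3 carries the same rule to best corrected and low luminance visual acuity ("alternative structures (e.g., heterogeneous autoregressive or heterogeneous compound symmetry, in this order) will be considered"), again with Kenward-Roger. Protocol 10.2 schedules both measurements monthly. SAP 7.1 and 7.3 treat the secondary analyses as descriptive and any testing as exploratory. SAP 7 and 7.1 set the primary level at 0.0125 one-sided per dose and 0.025 overall, with a Hochberg procedure.

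**The concern.** GA and visual acuity are progression measures. If each eye changes at its own fairly steady rate, the variance of change from Baseline grows with the square of time, and neighbouring visits stay closely correlated. Neither named structure has that shape. AR(1) lets the variance of change rise roughly in proportion to time, and compound symmetry holds it nearly flat. Heterogeneous variances repair this only in part. A model-based standard error inherits the misfit. Kenward-Roger adjusts for small samples under the fitted structure, not for having the wrong one.

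Two things are at stake: the width of the Month 12 visual acuity intervals and, on one reading of SAP 7.2, the one-sided level of the primary test. A separate question is whether the fallback offers anything new when only two visits are modelled.

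**Working it through.** **1. The plan's own figures.** Protocol 11.3 gives a 10% chance of reaching a 14% reduction under no effect, and 24.5% as the 0.0125 threshold. The implied standard error is 14/1.2816 = 10.92 points, or 24.5/2.2414 = 10.93. At a true 28% reduction, the chance of reaching 24.5% is Φ((28 - 24.5)/10.93) = 62.6%, against 63% stated. The design figures are coherent; the question is what happens if the fitted standard error is wrong.

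**2. Primary, two change scores.** Number of covariance parameters at two visits:
- Unstructured: 2 variances + 1 covariance = 3.
- Heterogeneous AR(1): 2 variances + 1 correlation = 3.
- Heterogeneous compound symmetry: 2 variances + 1 correlation = 3.

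Fitting both structures to a test matrix returned that matrix and the same maximised likelihood. They are one model, so the standard error and error rate do not change. This step needs no outside assumption.

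**3. Primary, three raw values.** Unstructured has 6 parameters and each fallback has 4, so misfit is possible. The documents give no correlations, baseline SD or reading error; all inputs here are assumptions. With t = (0, 0.5, 1) years, take the true covariance as S = B² + G²tt' + E²I, where B is the baseline SD, G the growth SD and E the reading error. The fitted structure M minimises log|M| + tr(M⁻¹S). With c = (-1, 0, 1):
- SE ratio = √(c'Mc / c'Sc)
- actual one-sided error = 1 - Φ(2.2414 × ratio)

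Example, scaled so that the 12-month change has variance 1, with B = 2.5 and noise 5% of that variance:
- True: 6.275 + 7.225 - 2(6.250) = 1.000.
- AR(1): 6.291 + 7.207 - 2(6.454) = 0.590; ratio 0.768; error 1 - Φ(1.721) = 4.3%.
- Compound symmetry: 6.349 + 7.297 - 2(6.549) = 0.548; ratio 0.740; error 4.9%.

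With noise at 40% of that variance:
- AR(1): variance 1.093; ratio 1.046; error 0.95%, which is conservative.
- Compound symmetry: variance 0.714; ratio 0.845; error 2.9%.

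A null simulation (80 vs 80, complete data, 400 runs) gave error rates for unstructured, AR(1) and compound symmetry of 1.5%, 5.0% and 6.3% at 5% noise, and 1.5%, 0.75% and 2.8% at 40% noise. Simulation error is about 0.6 points at a true rate of 1.25% and about 1.2 points at the highest rates.

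Range over B 0.5-1.1 mm and G 0.15-0.25 mm/yr:

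| Reading error | AR(1) ratio | Error | Compound symmetry ratio | Error |
|---|---|---|---|---|
| 0.02 mm | 0.725-0.749 | 5.2-4.7% | 0.717-0.736 | 5.4-5.0% |
| 0.06 mm | 0.812-0.931 | 3.4-1.8% | 0.748-0.797 | 4.7-3.7% |
| 0.10 mm | 0.931-1.097 | 1.8-0.7% | 0.793-0.865 | 3.8-2.6% |

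A wider grid used baseline SD 1.5-4 times the SD of change, noise share 2-40%, up to half of the remainder a random walk, and intercept-slope correlation 0-0.3. It gave 0.73-1.13 for AR(1) and 0.72-0.90 for compound symmetry. AR(1) crosses a ratio of 1 at a noise share of about one third with pure slopes, about one fifth if half the non-noise variance is a random walk, and near zero for a pure random walk.

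**4. Visual acuity, monthly.** Months 1 to 12 give 12 visits and 12 × 13/2 = 78 covariance parameters, assuming that all scheduled visits enter the model. The true covariance of change is G²tt' + E²I plus the variance of the baseline reading. Assumed: slope SD 6-10 letters/yr and reading SD 3-4.5 letters. SAP 5 averages Screening and Day 1 for baseline visual acuity when both exist, so both conventions were run. Month 12 SE ratios:
- Single baseline: AR(1) 0.826-0.936, compound symmetry 0.958-0.978.
- Averaged baseline: AR(1) 0.818-0.933, compound symmetry 0.945-0.964.

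The standard error is therefore about 6-18% too small under AR(1) and 2-6% under compound symmetry. A nominal 95% interval covers 2Φ(1.96 × ratio) - 1: about 89-93% under AR(1) and about 94% under compound symmetry.

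**The case against.** The strongest reply is that the primary is hardly exposed. The rule applies only if a 2×2 or 3×3 unstructured fit fails with about 160 (4 mg vs Sham) to 172 (2 mg vs Sham) subjects, which is unlikely. On the reading that SAP 3.2.1 favours, the fallback is the same model, so no error is inflated. That stands.

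A reader might infer that the fallbacks understate the standard error in general, that the primary test is therefore too liberal, and that 0.0125 and 0.025 do not hold. The documents do not support this. AR(1), which is tried first, can err in either direction, and the covariance figures that would settle it are not given. Every inflated primary error rate above belongs to the raw-score reading and is conditional on non-convergence.

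It is also fair to say that the secondary tests carry no alpha, that the rule's wording leaves other structures open, and that SAP 7 presents the 14% and 24.5% categories as guidelines based on the estimated reduction. With complete data, a wrong covariance mainly affects the standard error rather than that estimate.

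Finally, refitting the unstructured model is itself a reparametrisation. It is a remedy for numerical failure only, and at two visits heterogeneous Toeplitz would add nothing either. What the reply does not answer is the lack of a robust standard error when a structured covariance is actually used, as could happen in the visual acuity models.

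**Conclusion.** The point holds as a minor one. Its practical weight lies in SAP 7.3, where a 78-parameter fit may fail and the stated rule would then give Month 12 standard errors about 6-18% too small under AR(1) or 2-6% under compound symmetry. The consequence is intervals that are too narrow in an exploratory analysis. The sizes rest on assumed slope and reading SDs.

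For the primary, the two-change-score reading makes the fallback redundant but harmless. On the three-value reading, compound symmetry understated the standard error in every case tried (about 0.72-0.87 on the millimetre inputs, up to 0.90 on the wider grid), and AR(1) ranged from about 0.73 to 1.13. The 0.0125 level is not assured in that branch, but the branch is unlikely to be reached. A general claim that the primary error rate is inflated goes beyond what the documents show.

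**What to change.** In SAP 7.2, state that the response is change from Baseline in square-root GA at Months 6 and 12. In SAP 7.2 and 7.3, replace the fallback sentence with two steps:

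1. On non-convergence, refit the unstructured model with another parameterisation (such as Cholesky) and other starting values.
2. If a structured covariance is still used, report empirical (sandwich) standard errors in place of model-based Kenward-Roger. The two are alternatives and should not be combined.

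The cost is SAP wording, plus loss of the Kenward-Roger small-sample correction in the fallback branch only. With about 160 or more subjects per comparison that loss is small. No new data are needed, and the fallback change leaves the analysis untouched whenever the unstructured fit converges.

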### 7.3 ANALYSIS OF SECONDARY EFFICACY ENDPOINTS

Two secondary efficacy endpoints are pre-specified:

- Mean change in best corrected visual acuity (ETDRS letters) from Baseline to Month 12
- Mean change in low luminance best corrected visual acuity (ETDRS letters) from Baseline to Month 12

Secondary efficacy analysis will be conducted for ITT population for these pre-specified secondary endpoints. The analyses described above will also be repeated in a supportive manner for the PP population.

[figure not shown]
Descriptive tables will be provided for secondary endpoints based on the observed data, but due caution will be exercised in interpreting descriptive tables because of the potential impact of missing data. Sensitivity analyses of the secondary endpoints will also be performed (see Section 7.6).

Any hypothesis testing performed as part of analyzing secondary efficacy endpoints will be considered exploratory.

For analyses of the secondary endpoints, a Model for Repeated Measures (MRM) will be used to assess the differences between the treatment groups at month 12 visit. The model will be fitted by using restricted maximum likelihood (REML). The model will include Baseline VA (< 50 letters vs.  $\geq$  50 letters), size of the Baseline GA (< 4 disc area vs.  $\geq$  4 disc area), and pattern of FAF at the junctional zone of GA (none/focal vs. banded/diffuse) as used in the randomization as covariates. Fixed effects will include treatment, visit, part (Part 1 vs. Part 2), the Baseline VA (< 50 letters vs.  $\geq$  50 letters), size of the Baseline GA (< 4 disc area vs.  $\geq$  4 disc area), pattern of FAF at the junction zone of GA (none/focal vs. banded/diffuse), treatment by visit interaction, and the stratification factors by visit interactions for Zimura 2 mg vs. Sham control model. For Zimura 4 mg vs. Sham control model, the same fixed effects will be used excluding part (Part 1 vs. Part 2). An unstructured (co)variance structure will be used to model the within-subject errors. If this analysis fails to converge, alternative structures (e.g., heterogeneous autoregressive or heterogeneous compound symmetry, in this order) will be considered. The Kenward-Roger approximation will be used to estimate denominator degrees of freedom. Significance tests will be based on appropriate treatment contrasts at month 12.

CONFIDENTIAL

7.4	
-	
-	
_	

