#### 10.2.3.1 Day 1 Visit

##### Pre-injection

- [REDACTED]
- Protocol refraction and visual acuity (4 meters) using ETDRS chart (OU)
- [REDACTED]
- Low Luminance ETDRS Visual Acuity (OU)
- Goldmann Applanation Tonometry and Ophthalmologic Examination (OU)
- Randomization
- Randomized Treatment: Zimura™/Sham

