### **5 DEMOGRAPHIC AND OTHER BASELINE CHARACTERISTICS**

Descriptive statistics will be provided to document Baseline and on-trial comparability, including demographic information and treatment administration. No tests of significance will be carried out to compare treatment groups on Baseline data because any observed differences between them must be attributed to chance.

Descriptive statistics with respect to subject characteristics at Baseline will be displayed for the ITT population; if the PP and safety populations are different than the ITT population, demographic data will also be provided for these populations. When several measurements are available before the first administration of study drug, the Baseline value is the last available value prior to first dose, except for the Baseline visual acuity score which is the mean of the screening and Day 1 values, if both are available.

- The variables to be summarized are:
- Gender, ethnicity, race, iris color, age, current smoking status.
- Prior ocular history, both eyes (by MedDRA preferred term, including number and percentage of all subjects with at least one prior ocular history)
- Medical history (excluding ocular history) (by body system and preferred term, with number and percentage for both; including number and percentage of all subjects with at least one prior medical history)
- Prior surgeries/procedures (by body system and preferred term, with number and percentage for both; including number and percentage of all subjects with at least one prior surgery/procedure)
- Vital signs (height, weight, pulse, blood pressure)
- ECOG performance status
- Pregnancy test
- Visual acuity (ETDRS and Snellen equivalent), both eyes
- Low luminance ETDRS, both eyes
- Tonometry, both eyes
- ECG
- Ophthalmic exam, both eyes (motility, lids/lacrimal/lashes, conjunctiva/sclera, cornea, anterior chamber activity: cells, iris, pupils, lens status, vitreous haze, vitreous hemorrhage, posterior vitreous detachment, optic nerve, macula, retinal vessels, peripheral retina)

- Fundus autofluorescence (FAF) imaging assessments, both eyes
  - Localization of hypo FAF (Foveal, Extrafoveal, Ungradeable or no hypo FAF present)
  - Localization of peripapillary atrophy (Temporal only, Nasal and temporal, ungradeable or not applicable)
  - Hyper FAF pattern (Fine granular-punctate spots, Branching, Fine granular-dusty, Trickling, Reticular, Patchy, Banded, Focal, Not determinable/NA)

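### The models for change in BCVA and low-luminance BCVA (SAP 7.3) leave out the outcome's own continuous baseline, and the raw GA-area repeat has the same gap; a small, nearly free gain in precision goes unused

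*SAP*

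**What the plan says.** SAP 7.3 names two secondary endpoints, both change scores: BCVA and "Mean change in low luminance best corrected visual acuity (ETDRS letters) from Baseline to Month 12". One model form serves both. Its fixed effects are treatment, visit, the three randomisation factors, treatment by visit and strata by visit, with part added for 2 mg versus Sham. The factors are two-level: VA below versus at least 50 letters, GA below versus at least 4 disc areas, and "pattern of FAF at the junctional zone of GA (none/focal vs. banded/diffuse) as used in the randomization as covariates". No continuous baseline is listed. Protocol 11.6.4 also names only stratification factors, and Protocol 11.6.1 leaves the detail to the SAP.

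The missing baselines are collected. SAP 5 takes the last value before first dose, "except for the Baseline visual acuity score which is the mean of the screening and Day 1 values", and lists "Low luminance ETDRS, both eyes" among the variables to summarise. The protocol schedules low-luminance acuity on Day 1 but not at Screening.

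SAP 7.2 analyses the square root of area "To eliminate the dependency of GA growth rates on the Baseline lesion size". It then adds that "a similar analysis will be conducted using the observed GA area measurement". SAP 3.2.1 indicates that the analysed quantity is a change: "the primary analysis will require both Baseline and at least one post-Baseline GA measurement, to calculate a change score".

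**The concern.** A change score generally stays correlated with its own baseline, through regression to the mean or because progression depends on the starting level. A two-level cut of that baseline recovers only part of the explainable variance, and a cut of a different measure recovers less.

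Low-luminance BCVA is the more exposed endpoint. Only a coarse split of ordinary acuity represents its starting value, and its baseline is a single Day 1 reading. Baseline VA averages two readings, and subjects whose VA changes by 5 letters or more between them are excluded (Protocol 10.2.3). For raw area, the SAP itself says growth depends on lesion size, then adjusts for size only through one cut.

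The stake is precision. Protocol 11.3 has supportive efficacy endpoints feed the broader assessment of each dose, and the comparisons are modest: 80 versus 80 for 4 mg, and 26 + 40 = 66 versus 26 + 80 = 106 for 2 mg.

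**Working it through.** **The plan's own figures.** No precision or power figure is given for the secondary endpoints or the raw-area repeat. The primary figures in Protocol 11.3 reproduce. The thresholds imply a standard error of 14/1.2816 = 10.92 or 24.5/2.2414 = 10.93 percentage points. Power at a true 28% reduction is then Φ((28 − 24.5)/10.93) = 62.6%, against 63% stated, and the chance of reaching 14% is 90%. None of this moves, because the primary square-root model is not at issue.

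**Inputs for the acuity endpoints (all assumed).**
- ρ, correlation of baseline with Month 12: 0.6–0.9
- k, SD at Month 12 divided by SD at Baseline: 1.0, 1.1, 1.2
- p, share of subjects below 50 letters: 20–50%
- r, correlation of baseline BCVA with baseline low-luminance BCVA: 0.5–0.7

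**Formulas.**
- Share of change-score variance explained by own baseline: R² = (1 − ρk)² / (1 + k² − 2ρk), which is (1 − ρ)/2 at k = 1.
- Fraction of R² kept by a cut at p: f = φ(z_p)² / (p(1 − p)), which is 0.49 at 20% and 0.64 at 50%. For low-luminance BCVA, multiply f by r² (0.25–0.49).
- Further fall in residual variance from adding the continuous baseline: 1 − (1 − R²)/(1 − fR²).
- Fall in interval width: 1 − √(1 − variance reduction).

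Example, BCVA with ρ = 0.6, k = 1, p = 20%: R² = 0.20, and 1 − 0.80/(1 − 0.49 × 0.20) = 11.3% of variance, or 5.8% of width.

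**Reduction in residual variance.**

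| k | ρ | BCVA | Low-luminance BCVA |
|---|---|---|---|
| 1.0 | 0.6 | 8.3–11.3% | 14.7–18.0% |
| 1.0 | 0.9 | 1.9–2.6% | 3.5–4.4% |
| 1.1 | 0.6 | 5.2–7.1% | 9.3–11.6% |
| 1.1 | 0.8 | 1.2–1.7% | 2.2–2.8% |
| 1.1 | 0.9 | 0.02% | 0.03–0.04% |
| 1.2 | 0.6 | 3.0–4.2% | 5.5–7.0% |
| 1.2 | 0.8 | 0.1–0.2% | 0.2–0.3% |
| 1.2 | 0.9 | 0.8–1.2% | 1.6–2.0% |

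The largest width reductions are 1 − √(1 − 0.113) = 5.8% for BCVA and 1 − √(1 − 0.180) = 9.4% for low-luminance BCVA. The smallest are essentially zero.

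**Cost of the covariate.** One extra covariate costs about 1/(160 − 6 − 1) = 0.65% of variance for 4 mg and 1/(172 − 7 − 1) = 0.61% for 2 mg. A simulation at 80 versus 80 (r = 0.6, 35% below 50 letters) gave these net low-luminance variance gains:
- ρ 0.6, k 1.0: 14.6%
- ρ 0.8, k 1.0: 6.4%
- ρ 0.8, k 1.1: 1.7%
- ρ 0.9, k 1.1: −0.7%

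**Raw GA area (simulated).** Square-root growth was taken as independent of baseline, which is the SAP's premise. Assumed inputs were lognormal baseline area with median 2.5–4.5 disc areas and log SD 0.4–0.6, limited to 1–7 disc areas; growth CV 0.5–0.9; and mean growth 0.1–0.3 in root disc areas. Adding continuous area to the 4-disc-area cut removed a further 0.6–6.8% of residual variance, or 0.3–3.5% of width. Widening the limits to 0.5–10 disc areas gave 0.9–9% of variance. A second simulation, with a normal baseline on the root scale and cuts at its median and 70th percentile, gave 1.2–5.3% of the standard error.

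**The case against.** The case for leaving the plan alone is that nothing that decides the trial changes. SAP 7.1 calls the secondary analyses descriptive, SAP 7.3 calls any testing exploratory, and the 14% and 24.5% guideline concerns GA growth only. That is true, and it limits the weight of the point.

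The top of the range is also favourable: it needs ρ = 0.6 and equal SDs. Protocol 10.2.3 restricts acuity to 20/25–20/320 on Day 1 while Month 12 is unrestricted, which favours k above 1 and a smaller gain. The formulas also give no credit to GA size and FAF pattern, which are already in the model, so they may overstate the gain. These objections stand, and they are why the lower end is put at nil or slightly negative.

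An unstructured covariance does not close the gap. If Baseline were a response visit with free treatment-by-visit terms, the Month 12 minus Baseline contrast would equal the change-score analysis for complete data. Only a common baseline mean across arms would help, and the SAP states none. The raw-area covariate does apply only where the response is post-baseline change, and SAP 7.2 does not write that model out.

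Finally, SAP 7.4 is blacked out, so the claim that baseline low-luminance BCVA is in no model covers the visible text only. The SAP 7.3 list of fixed effects is complete as written, so the gap there remains.

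**Conclusion.** The point holds as a worthwhile refinement with no bearing on validity. On the assumed inputs, intervals would narrow by about 0–6% for BCVA and 0–9% for low-luminance BCVA. For raw GA area the figure is about 0.3–3.5%, reaching about 5% under the wider assumptions. Low-luminance BCVA has most to gain. The worst case is a loss of about 0.6–0.7% of variance, when ρk is near 1. Confidence in the gap is high; confidence in its size is medium, because the documents supply none of the correlations or SDs.

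**What to change.** Before unmasking, amend SAP 7.3 to add continuous baseline BCVA letters to the BCVA model and continuous baseline low-luminance letters to the low-luminance model, each with its visit interaction. Keep the randomisation strata, and part in the 2 mg model. In SAP 7.2, write out the raw-area model and, where its response is post-baseline change, add continuous baseline GA area with its visit interaction. Leave the primary square-root model as it is.

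State which visits enter the acuity models: the addition is 2 parameters if only Months 6 and 12 enter, and 12 if every monthly visit to Month 12 does.

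The cost is SAP wording, with no new data. Protocol 11.6.4 mentions only stratification factors, so the SAP should note the added covariate as detail that Protocol 11.6.1 leaves to it. Choosing the covariate after unmasking would invite the charge that it was selected on the results.
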